3.3 Rationale for Concurrent Cisplatin and RT

Biologically, cisplatin is a known radiosensitizer, with both additive and synergistic potentiation of radiation. Platinum potentiates radiation-induced cell injury through a number of putative mechanisms. These agents act via formation of DNA cross links resulting in DNA double-strand breaks. When cisplatin is integrated into DNA adjacent to a radiation-induced single cell strand break, it can make the break more difficult to repair and thus lead to cell death [15,16]. In addition, cisplatin increases cellular platinum uptake [16], and enhance formation of toxic platinum intermediates [17]. The potentiation of radiation-induced cell injury appears under both oxic and hypoxic conditions [18].

Preclinical studies have shown that the combination of cisplatin and RT delivers the maximum ex-vitro stress response needed to stimulate HRR repair, compared to cisplatin or RT when delivered individually. Mouse embryo fibroblast cells with mutated DNA repair pathways were measured for responses after cisplatin, radiation and combination treatments. The combination treatment showed that inhibition of the HRR pathway resulted in super additive effects, compared to cisplatin or RT alone [19].

Concurrent cisplatin and radiation treatment is standard of care in the definitive treatment of advanced head and neck as well as cervical cancer [20-30]. A large meta-analysis has established the survival benefit of concurrent chemoradiation versus RT alone for head and neck cancer [27]. The efficacy and safety profile of concurrent cisplatin and RT in cervical cancer has also been well established in randomized trials [20-24]. The toxicities of concurrent cisplatin and RT are specific to the irradiated site but are generally tolerable. Adverse events among cervical cancer patients who received both cisplatin and RT included 12% grade 3 leukopenia, 1.1% thrombocytopenia, 5.6% other hematologic toxicities and 4.5% grade 3 gastrointestinal toxicities. Grade 2 toxicities included 14.7% leukopenia, 2.3% thrombocytopenia, 15.3% other hematologic toxicities and 15.9% gastrointestinal toxicities. No treatment-related deaths were reported in these trials.

Whereas q3 week dosing (100 mg/m²) of cisplatin has been shown to result in significant toxicity in patients with laryngeal cancer when delivered concurrently with RT (40), lower weekly doses (30-50 mg/m²) has been well tolerated [29,30]. Based on these data, we plan to utilize weekly cisplatin (\pm 3 days) at 25 mg/m² prior to and after RT. During RT, the dose of cisplatin will be weekly (\pm 3 days) 25 mg/m².

Following the completion of RT, pending no toxicities, but prior to the week 12 post RT evaluable timepoint, patients will either continue to receive cisplatin or until POD, based on MD discretion.

3.4 Evidence for Cisplatin and Biomarkers of Response in Triple Negative Breast Cancer

Currently, there is no standard chemotherapy for the treatment of metastatic or recurrent triple negative breast cancer. Generally, these patients receive a single agent chemotherapy, of which there are many options. The standard chemotherapy treatment for breast cancer patients with BRCA1 or BRCA2 mutations are the same as those treatments for sporadic breast cancer patients, which do not include platinum chemotherapy for non-metastatic disease. The “BRCA-ness” features of sporadic TNBC are suggestive of sensitivity to interstrand crosslinking agents such as platinum chemotherapy [31]. There is mounting preclinical as well as early clinical evidence suggesting benefits of platinum chemotherapy in patients with BRCA1 and BRCA2 mutations and TNBC.

Single-agent weekly cisplatin is not routinely used in breast cancer, but there is growing use of cisplatin in triple negative breast cancer because patients with BRCA mutations appear to be uniquely sensitive to cisplatin in non-randomized trials, and the broader array of TNBC patients with HRR defects (but no known BRCA mutations) are thought to be sensitive to cisplatin. Several clinical studies have evaluated the role of platinum chemotherapy among TNBC patients, including those with and without BRCA1 or BRCA2 mutations. A Dutch study demonstrated that patients with BRCA-like genomic profiles observed a greater benefit with high dose platinum chemotherapy vs conventional chemotherapy, compared to patients with non-BRCA-like tumors [32]. A proof-of-concept neoadjuvant study from Poland involving 12 breast cancer patients who were BRCA1 mutation carriers demonstrated a pCR of 83% following treatment with 4 cycles of single-agent cisplatin 75 mg/m² [33]. Two studies, both from the Dana-Farber Cancer Institute, evaluated neoadjuvant cisplatin at 75 mg/m² for four cycles. Silver et al reported a response rate of 21% in a study of 28 unselected TNBC [34], whereas the larger n=51 patient study by Ryan et al [35], in which patients also received bevacizumab every 3 weeks for three cycles, demonstrated a pCR rate of 15% among patients without BRCA mutations. Factors associated with good cisplatin response in the Silver et al. study included young age (p=0.001), low BRCA1:mRNA expression (p= 0.03), BRCA1 promoter methylation (p=0.04), p53 nonsense or frameshift mutations (p=0.01), and a gene expression signature of E2F3 activation (p=0.03), suggesting that biomarkers other than BRCA1 may be predictive for cisplatin response [34].

A study of preoperative cisplatin in early-stage breast cancer patients with germline BRCA1 mutations demonstrated high rates of pathologic complete response (72%) [36]. Others have shown high rates of pathologic complete response in mutation carriers, including a neoadjuvant trial of gemcitabine, carboplatin and iniparib. Among 17 enrolled women with germline BRCA1 or BRCA2 mutations, 15/17 (88%) achieved a pathologic complete response (pCRs) or had minimal residual disease at the time of surgery [35].

Recently published results from the GepardSixto (GBG 66) trial also suggest a beneficial role for platinum chemotherapy in TNBC. This trial included 595 patients with HER2+ and TNBC. All patients received paclitaxel and non-pegylated-liposomal doxorubicin. HER2+ patients also received trastuzumab and lapatinib, whereas TNBC patients also received bevacizumab. All patients were randomized 1:1 to receive concurrent carboplatin or not, stratified by subtype. Among the TNBC patients, pCR rates increased by 20%; 84 (53.2%) of 158 patients achieved a pCR with carboplatin,

compared with 58 (36.9%) of 157 without ($p=0.005$). This effect was not seen among the HER2+ patients, 45 (32.8%) of 137 of whom achieved a pCR with carboplatin compared with 50 (36.8%) of 136 without ($p=0.58$) [37]. The advantage seen with carboplatin was driven by patients with triple negative disease. The regimen was very toxic, with about 50% of patients receiving carboplatin having to discontinue treatment due to adverse events.

The preliminary results of CALGB/Alliance 40603 study (presented at the 2013 San Antonio Breast Cancer Symposium) also support these findings. In this study, 454 patients with stage II/III TNBC were randomized to standard neoadjuvant chemotherapy or chemotherapy plus either carboplatin, bevacizumab, or the combination of carboplatin/bevacizumab. Patients were randomly assigned in a 2×2 schema to receive weekly paclitaxel plus dose-dense anthracycline/cyclophosphamide +/- either the addition of bevacizumab or the addition of carboplatin. For patients receiving carboplatin, 60% achieved a pCR, compared to 46% of those who did not carboplatin - an increase of 76% ($p=0.0018$). Defined by no disease in the breast or axilla, pCR rates were 54% with carboplatin vs 41% without carboplatin, a 71% increase ($p=0.0029$). When the combination of carboplatin and bevacizumab were used in addition to chemotherapy, 67% of patients achieved a pCR, however, a significant treatment interaction between the two drugs was not shown. Bevacizumab resulted in a greater frequency of adverse effects, as did the combination of bevacizumab and carboplatin. Patients receiving carboplatin were more likely to experience neutropenia and thrombocytopenia.

Finally, the PrECOG 0105 study included 80 TNBC and BRCA1/2 mutated patients treated with neoadjuvant carboplatin, gemcitabine and iniparib [38]. Pathologic CR was achieved in 36% of the overall population, 47% in the BRCA1/2 mutated population and 56% in triple negative patients who also had BRCA 1/2 mutations. The toxicity profile was more favorable than that of the Gepar Sixto regimen, with myelosuppression (grade 3 or 4 neutropenia in 49%) and elevations in liver enzymes (grade 3 in 24%).

Whereas the aforementioned trials evaluated platinum chemotherapy in the neoadjuvant setting, the efficacy of platinum chemotherapy has also been studied in metastatic TNBC patients. TBCRC 009 was a multicenter single-arm phase I study of single-agent platinum in 86 patients with metastatic TNBC [39]. Patients received cisplatin 75mg/m² or carboplatin AUC=6 every 3 wks, by physician choice. The objective response rate (ORR) was 30.2% overall, including 4 CR (4.7%), 22 PR (25.6%). The ORR was 54.5% vs. 19.7% in BRCA1/2 carriers (n=11) vs. non-carriers (n=66); ($p=0.02$). Six long-term responders remain disease-free at median follow up of 4 yrs, 3 of whom stopped treatment after 6 cycles. Exploratory subgroup analysis of RR: Cisplatin 37%, Carboplatin 23%; 1st line therapy 31.7%, 2nd line therapy 20%. 33% of pts progressed by 6 weeks, but 33% remained on study for ≥ 6 mos. 51 treatment-related grade 3/4 toxicities occurred. 2 patients had grade 4 toxicities (neutropenia (1) and hypertension (1)), while the others were grade 3 (fatigue (8), neutropenia (6), anemia (5), hyponatremia (4)).

In a subsequent analysis presented at the ASCO 2014 Annual Meeting, predictors of response to platinum chemotherapy were assessed, including p63/p73 expression by RT-PCR as a predictor of response. Tumor-based exploratory studies included gene expression (GE) profiling, PIK3CA and p53 mutational status, and homologous recombination deficiency (HRD) assays correlating with

BRCA1/2 inactivation. All biomarkers *except* the HRD assays failed to predict responses to platinum chemotherapy. Types of HRD assays performed included Loss of Heterozygosity (LOH), Telomere Allelic Imbalance (tAI), and Large-scale State Transition (LST). Among the small group of 22 patients with available tissue, scores in all of the HRD assays were higher in BRCA1/2 carriers than non-carriers, and in responders than non-responders (HRD-LST responders vs. nonresponders, $p=0.0016$).

Birback et al. have also suggested that the number of subchromosomal regions with allelic imbalance extending to the telomere [N(tAI)] is predictive for pathologic response to preoperative cisplatin treatment in sporadic TNBC patients. They found an inverse relationship between BRCA1 expression and N(tAI), suggesting that N(tAI) could be a genomic measure of DNA repair pathway defects and thereby identify patients who could benefit from cisplatin therapy[40]

The results from a clinical trial performed at Washington University provide the most compelling preliminary evidence for this proposed study [41]. In this trial, neoadjuvant pre-operative cisplatin + RT were administered for locally advanced triple-negative breast cancer patients, all of whom received modified radical mastectomy as definitive surgical treatment. Response was analyzed by HRR status, utilizing the functional HRR assay developed by Powell et al. Among the 10 patients enrolled to date, 6/10 show pathologic CR, of whom 5/6 (83%) were HR-defective. Given the small number of patients accrued to this trial, further validation of the results are required, and is therefore the aim of this proposed protocol.

3.5 Immune Correlates

A large body of research using experimental animal models indicates that the immune system controls the development of cancer through immune surveillance mechanisms[42]. Histologic analyses of solid malignancies reveal that they are infiltrated by various cells of the innate and adaptive immune system [43]. Therapeutic modulation of the immune system for clinical benefit in cancer patients has been demonstrated by numerous modalities, including antibody blockade of inhibitory molecules, adoptive T cell transfer, and autologous cell-based vaccines [44-47]. A recent large-scale meta-analysis of the correlation of tumor infiltrating T cells with survival clearly establishes that a relative high density of TH1 and cytotoxic memory T cells correlated with a favorable prognosis in the majority of cancers [48].

Tumor infiltrating lymphocytes (TILs) may be a useful histological predictor of benefit from chemotherapy in breast cancer patients, although it has not been established whether or not response to chemotherapy would be specific to a class of chemotherapy. Specific to breast cancer, the evaluation of TILs has been shown in the GeparSixto (GBG 66) trial to be relevant for response to chemotherapy in triple negative and Her2-positive early breast cancers [37,49]. In this analysis, a lymphocyte predominant pattern of infiltrate was predictive of a complete pathologic response to neoadjuvant chemotherapy. Similarly, the association of TILs and response to trastuzumab and chemotherapy (epirubicin/cyclophosphamide with docetaxel +/- capecitabine) was evaluated in 156 HER2+ patients from the neoadjuvant GeparQuattro trial [50]. TILs were associated with higher responses to the trastuzumab and chemotherapy combination, and tumor-mediated immunosuppression was evident in the lymphocytic infiltrate, with PD-1 and IDO1 significantly

predictive of trastuzumab benefit.

The prognostic value of TILs has also been validated in a combined analysis of two Phase III randomized adjuvant breast cancer clinical trials [37,51-54]. In these studies, the percentage of intratumoral and stromal lymphocytes in pre-treatment tumor biopsies was found to be an independent predictor of pCR in both the training and validation cohorts. Higher TIL pathologic scores were associated with a better prognosis: for every 10% increment in stromal TIL, a 14% reduction of risk for recurrence or death was observed ($p=0.02$), and for every 10% increment in intratumoral TIL, a 28% risk reduction was seen ($p=0.06$). Multivariate analysis confirmed stromal TIL to be an independent prognostic marker of disease-free survival.

Collectively, these data suggest that the natural course of breast cancer as well as the response to therapy is linked to the degree by which the tumor is recognized by the immune system. Response to radiotherapy may be also be predicted by the level of TIL, however data supporting this in breast cancer is scant. In squamous cell carcinoma of the head and neck as well as rectal cancer however, TILs can predict response to combination chemoradiotherapy [55,56]. The induction of an immune response by radiotherapy may also have important consequences. Several studies have shown the various mechanisms by which RT stimulates the immune system. One effect of localized tumor irradiation is the exposure of a large amount of tumor antigens in the form of necrotic and apoptotic tumor cells [57]. The contexts in which these antigens are presented to the immune system are also impacted by tumor irradiation. Tumor radiotherapy leads to an inflammatory tumor microenvironment by inducing the expression of several proinflammatory cytokines [58,59]. In addition, upregulation of major histocompatibility molecules and costimulatory molecules can potentiate effector cytolytic T cell responses [59].

The pretreatment biopsy planned in this study will allow for the comprehensive assessment of TIL which will be correlated to response. This will provide important insight into the role of the tumor immunity in the response to chemoradiotherapy. In addition the assessment of homologous recombination can also factor into the endogenous response of the immune system to the tumor as well as response to therapy. The effect of homologous recombination on tumor immunity is not well characterized, however the induction of microsatellite instability as a pathway of carcinogenesis has clearly been linked to tumor immune response [60]. Tumor cells with deficient DNA mismatch repair develop microsatellite instability and the resulting tumors are densely infiltrated by TILs [61]. It is suggested that mismatch repair deficiency leads to numerous insertion/deletions that ultimately translate to the generation of tumor-specific neopeptides that can then be recognized by the immune system [62]. Radiation administered to a tumor with an underlying homologous recombination defect may lead to significant “epitope spreading” resulting in the induction of an immune response against newly recognized tumor associated antigens. This study will begin to address the immune consequences of tumor genomic instability.

3.6 Circulating Tumor DNA (ctDNA) Sensitivity

In a number of clinical settings, circulating tumor DNA(ctDNA) has emerged as a promising biomarker of disease burden that in some cases provides greater sensitivity than imaging. Furthermore, ctDNA in patients with very high disease burdens can also be used to track emergence of treatment resistant subclones[63,64]. However, ctDNA in the setting of cisplatin and radiation for recurrent/metastatic breast cancer remains entirely uninvestigated and the sensitivity of detection is unknown.

When feasible, we will collect 1 tube of blood (8-10mL) in EDTA or Streck tubes[65] for ctDNA analysis at the scheduled time periods of blood sample collection as outlined in Section 10.0. The plasma will be isolated through centrifugation (820xg x 10 minutes, then 16,000g x 10 minutes) and stored at -80C for analysis. Using known somatic mutations obtained through exome resequencing data of tumor samples, mutant alleles in ctDNA will be assessed through amplification of loci from extracted cell free DNA and massively parallel sequencing or detected through digital droplet polymerase chain reaction (ddPCR). We will use a data-analysis pipeline wherein incidentally sequenced germline variants will be filtered out of sequencing analyses using matched DNA from buffy coat DNA. Thus, germline alterations will not become apparent to researchers.

4.1 OVERVIEW OF STUDY DESIGN/INTERVENTION

4.2 Design

This is a single-arm Phase II trial testing the efficacy of concurrent cisplatin and radiation in breast cancer patients with measurable metastatic or locally recurrent tumor, based on HRR status as determined by the MSK-HRR assay. Prior to study enrollment, all patients will require assessment by the radiation oncologist and medical oncologist. Patients will receive a baseline PET-CT +/- MR for evaluation of the tumor to be irradiated and to assess extent of disease systemically. If unavailable within the time specifications of the study, the PET-CT +/- MR will be performed after study registration. Biopsy of the tumor to be irradiated will be performed. Fresh tissue specimens will be sent to the laboratory of [name] for performance of the MSK-HRR Assay. Results from the functional assay will be utilized towards the primary endpoint. Additional unutilized tissue will be sent to the Immune Monitoring Facility Laboratories for TIL analyses to be conducted by [name]. Bloodwork will be sent to the lab of [name] for ctDNA analyses. After the biopsy, patients will undergo simulation for palliative radiation to the tumor site. Following simulation, patient will initiate a 25 mg/m² infusion of cisplatin once a week \pm 3 days. The starting dose will depend on baseline laboratory results within 28 days prior to registration. Following 1-2 weeks of cisplatin, RT will be initiated. Weekly cisplatin (\pm 3 days) will be continued and delivered concurrently with RT. After the completion of RT, weekly cisplatin (\pm 3 days) will be continued until disease progression or until assessment of treatment response at Week 12 post RT (+/- 2 weeks), based on MD discretion. Patients whose HRR status is found to be inevaluable by the MSK assay will not be included in the study and will be replaced by eligible patients.

At Week 12 (12 \pm 2 weeks after RT; with strong recommendation at 12 weeks), repeat imaging with the same imaging methods used for baseline assessment will be performed. Treatment response will be

determined by either PRC or RECIST 1.1.

We estimate accrual will occur at the rate of 15 patients per year. It will take 3.5 years to accrue the total of 54 patients. Patients will be followed up to 24 weeks after completion of RT to determine all study endpoints. Clinical follow-up will continue until death.

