4.3 Intervention

4.3.1 Cisplatin Administration

Cisplatin treatment should be initiated following study registration. The starting dose of cisplatin is established as 25 mg/m² ivpb once a week (\pm 3 days) for 1-2 weeks prior to radiation. Dose modification following the first dose of cisplatin is subject to the discretion of the treating physician. Dosing calculation guidelines will follow MSKCC policies described on the website:

http://mskweb5.mskcc.org/intranet/shared/pharmacy/guidelines/Chemo_Guidelines/Manuals/Cisplatin.html

Cisplatin may be initiated immediately following simulation but prior to first radiation fraction. The rationale is so that the patient may initiate a form of treatment while waiting 1-2 weeks for radiation treatment planning to be completed.

Cisplatin may cause myelosuppression or other known non-hematologic toxicities. Following the completion of RT, pending no toxicities, but prior to the week 12 post RT evaluable timepoint, patients will continue to receive cisplatin based on MD discretion, or until POD.

The starting (first) dose of cisplatin will be 25 mg/m² ivpb once a week (\pm 3 days). Following the first dose of cisplatin, a CBC will be drawn once a week (\pm 3 days) prior to treatment to ensure treatment parameters are met. A comprehensive panel and Mg++ level will be obtained on D15 (\pm 3 days) of every cycle of cisplatin; these values will inform the dose for the following cycle of cisplatin. The length of one cycle of Cisplatin is 21 days. If cisplatin is withheld, the cycle count for treatment is also held. Based on the laboratory values drawn from the prior week's bloodwork, if the following parameters are met, cisplatin should be held as directed.

- If ANC is <1,000 mcL and/or platelets are <100,000 mcL, withhold cisplatin therapy for one week and repeat measurements. Physicians have the option of administering growth factor support during the time when ANC < 1,000 mcL or platelets are < 100,000 mcL. The treating MD may modify the subsequent cisplatin doses at their discretion. If there is a delay of 3 consecutive weeks of treatment due to toxicity, then the patient must discontinue protocol therapy and be removed from the study.
- If the ANC is still <1,000 mcL or platelets are 75,000-99,000 mcL, then hold weekly cisplatin again until the ANC is >1,000 mcL and platelets are >100,000 mcL. The treating MD may modify the subsequent cisplatin doses at their discretion.

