- If serum creatinine is >1.5 mg/dL, delay treatment, provide intravenous hydration and check 12 or 24 hour creatinine clearance, serum creatinine and electrolytes after 24 hours. If the serum

creatinine is ≤ 1.5 mg/dL and creatinine clearance ≥ 60 cc/min, may give full dose of cisplatin. If serum creatinine is 1.6-1.9 and creatinine clearance is between 30-60 cc/min, cisplatin can be given at the discretion of the treating physician. If serum creatinine is >2 OR creatinine clearance is <30 cc/min, hold cisplatin.

- If the patient develops any non-hematologic grade 3-4 toxicity, cisplatin will be held until toxicity is reduced to grade 2 or less. Dose reduction is permitted at the discretion of the treating physician. If a patient experiences grade 2 toxicity (with exception of alopecia) that lasts >2 weeks, cisplatin will be held and dose reduction recommended at discretion of the treating physician. Cisplatin will be discontinued if greater than grade 2 toxicity persists following 2 dose reductions.
- If the patient develops an intercurrent illness (e.g. infection) that, in the opinion of the treating medical oncologist, mandates a delay of cisplatin therapy, the intercurrent illness must be resolved within a time frame such that no more than 2 weekly doses of cisplatin are withheld. If therapy must be withheld for a longer period of time, the patient will be removed from the study.
- Following the completion of RT but prior to the week 12 post RT evaluable timepoint, patients will continue receiving cisplatin based on MD discretion. The dose and schedule of cisplatin after the completion of RT will be at the discretion of the treating MD. If there is a delay of 3 consecutive weeks of treatment, then the patient must discontinue protocol therapy and will be removed from study. Continuation of cisplatin and the dose and schedule of cisplatin after Week 12 post RT assessment will be at the discretion of the treating MD.
- Note: Disruption to the cisplatin treatment schedule for 3 weeks due to unforeseen circumstances, holidays or the patient being on vacation is permitted and will be reviewed on a case-by-case basis.

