6.1 CRITERIA FOR SUBJECT ELIGIBILITY

6.2 Subject Inclusion Criteria

- Histologically-confirmed invasive triple negative breast cancer (ER <1%, PR <1%, her-2-neu 0-1+ by IHC or FISH-negative) or as determined by MD discretion
- Radiation to the recurrent or metastatic site is clinically indicated and would be considered standard care for palliation or for locoregional control
- Age \geq 18 years
- Tumor to be irradiated is measurable by RECIST 1.1 or PRC (see Appendix 1 and Section 12.0)
- Willingness to undergo tumor biopsy prior to initiation of treatment
- Life expectancy greater than 6 months
- ECOG performance status 0-2
- Any prior chemotherapy is allowed including prior treatment with platinum-containing chemotherapy
- Prior treatment with FDA-approved or investigational biologics or novel molecularly target therapies, including oral or IV formulations, are permitted. Patients must be off prior targeted therapy for at least 14 days prior to study biopsy.

- Use of an effective means of contraception in women of child-bearing potential
- Ability to comprehend and sign informed consent
- Adequate organ and marrow function within 14 days prior to study entry, defined as:
 - Absolute neutrophil count (ANC)>1000/mm³
 - Hemoglobin >9 gm/dl
 - Platelets >100,000/mm³
 - Serum creatinine <1.5 mg/dl OR creatinine clearance of \geq 50 cc/min
 - SGOT/SGPT<2.5X institutional ULN (<5X ULN if known liver metastases)

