8.1 PRETREATMENT EVALUATION

- Within 28 days prior to study registration:

- Evaluation by Radiation Oncology
- Evaluation by Medical Oncology
- PET-CT +/- MR performed at MSKCC
- Complete Blood Count
- Comprehensive Metabolic Panel with Magnesium
- Serum Pregnancy Test for Women of Child Bearing Potential
- Biopsy of target tumor

- After study registration but before cisplatin weekly dose #1:
 - PET-CT +/- MR (only if imaging was not done prior to study registration or not done at MSKCC)
 - Biopsy of target tumor (if not completed prior to registration)
 - Peripheral blood sample for immunologic correlate studies, ctDNA, and/or BRCA mutation status (if unknown prior to study registration).

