10.0 EVALUATION DURING TREATMENT/INTERVENTION

The Table below illustrates the interventions and treatments required at specific time intervals for the study. All evaluations can be performed as frequently as clinically indicated.

Study Requirement	Within 28 days prior to Study Registration	After Study Registration/Before Cisplatin Dose #1	During RT	D1 of Cisplatin Cycle	D8 of Cisplatin Cycle	D15 of Cisplatin Cycle	12+2 weeks after RT	q6 months after RT
Evaluation by Radiation Oncology	X ¹¹		X ¹⁰				X ^{4,11}	X ^{3,4,11}
Evaluation by Medical Oncology ¹¹	X			X ⁸			X ⁴	X ^{3,4}
PET-CT +/- MRI	X	X ¹					X	X ³
Biopsy of Target Tumor	X	X ¹²						
CBC ⁵	X		X	X	X	X	X	X
Mg++, CMP ⁵	X					X		
Pregnancy Test	X							
Peripheral blood sample for immunologic correlate studies, ctDNA, and/or BRCA mutation status		X ²	X ⁹				X	
Cisplatin Administration ⁷			X ⁶	X	X	X		
Toxicity Assessment			X ¹³	X ¹³				

¹ Only if imaging was not done prior to study registration or not performed at MSK

² Obtain only if BRCA 1 or 2 mutation status is unknown at baseline. BRCA 1 or 2 mutation status may also be obtained from the tissue biopsy at baseline. Bloodwork for immune correlates and ctDNA will be obtained at baseline.

³ Recommended but not required.

⁴ May be performed by either radiation oncologist or medical oncologist, but both visits are not required.

⁵ Except at baseline, CBCs will be checked once a week (± 3 days) during cisplatin but prior to administration. Mg2+ and serum chemistries will be obtained on D15 (± 3 days) of every cisplatin cycle.

⁶Radiation will begin following 1-2 weeks of cisplatin. Weekly cisplatin (\pm 3 days) will be continued and delivered concurrently with RT.

⁷ The length of one Cisplatin cycle is 21 days. Cisplatin is administered on D1, D8 and D15 (\pm 3 days) of every cycle. Following the completion of RT, pending no toxicities, but prior to the week 12 post RT evaluable timepoint, patients will continue to receive cisplatin or until POD, based on MD discretion.

⁸ The medical oncologist will evaluate the patient on D1 of each cisplatin cycle. The patient will be assessed for toxicities and will be recorded on a ClinDoc Toxicity form, complete with grade, attribution, start, and stop dates.

⁹ Bloodwork will be obtained during the last week of RT for immune correlates and ctDNA.

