15.1 RESEARCH PARTICIPANT REGISTRATION AND RANDOMIZATION PROCEDURES

15.2 Research Participant Registration

Confirm eligibility as defined in the section entitled Inclusion/Exclusion Criteria. Obtain informed consent, by following procedures defined in section entitled Informed Consent Procedures. During the registration process registering individuals will be required to complete a protocol specific Eligibility Checklist. The individual signing the Eligibility Checklist is confirming whether or not the participant is eligible to enroll in the study. Study staff are responsible for ensuring that all institutional requirements necessary to enroll a participant to the study have been completed. See related Clinical Research Policy and Procedure #401 (Protocol Participant Registration)

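### Baseline labs may be 28 days old under 4.2, 8.1 and Section 10 but only 14 under 6.2, and the creatinine hold lacks required prior-week chemistry at cycle 1 D1 and every D8

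*Combined protocol and SAP*

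**What the plan says.** **Baseline.** Section 4.2 says of cisplatin: "The starting dose will depend on baseline laboratory results within 28 days prior to registration". The same section and 4.3.1 set the first dose at 25 mg/m². Section 8.1 lists the CBC and the metabolic panel with magnesium under "Within 28 days prior to study registration", together with imaging, visits and biopsy. The Section 10 table marks both tests in its 28-day column and neither in the column between registration and the first cisplatin dose.

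Section 6.2 instead requires "Adequate organ and marrow function within 14 days prior to study entry", and its limits include one for creatinine or creatinine clearance. Section 15.2 places the eligibility check at registration: "Confirm eligibility as defined in the section entitled Inclusion/Exclusion Criteria".

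**On treatment.** Sections 4.3.1 and 9.0 and footnote 5 of Section 10 ask for a weekly CBC but less frequent chemistry: "Mg2+ and serum chemistries will be obtained on D15", with a window of ±3 days. Section 4.3.1 says of the D15 results that "these values will inform the dose for the following cycle of cisplatin". It introduces the hold rules with "Based on the laboratory values drawn from the prior week's bloodwork", and one of those rules is "If serum creatinine is >1.5 mg/dL, delay treatment".

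**The concern.** There are two linked problems.

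First, the eligibility criterion and the schedule give different lab windows. A coordinator working from 8.1 or the table can collect a panel that completes the schedule but does not show eligibility under 6.2. The likely results are an eligibility deviation or a late repeat test. The 4.2 sentence adds to the confusion: it makes the starting dose depend on 28-day labs, but the dose is fixed and no rule links it to a lab value.

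Second, the renal hold needs a recent creatinine that the schedule does not supply for some doses. Section 11.2 describes cisplatin nephrotoxicity as cumulative and requires renal function to normalize before further dosing. Without a current value, that requirement and the 1.5 mg/dL hold are applied to an old result or not at all. The blood-count holds do not have this problem, because a CBC is scheduled weekly.

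**Working it through.** The plan states no figure to reproduce. The check is a comparison of windows followed by day counts.

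**Inputs.**
- Lab window *w*: 28 days (4.2, 8.1, Section 10) or 14 days (6.2).
- Dosing days: D1, D8 and D15 of a 21-day cycle (Section 10, footnote 7), so offset *d* = 0, 7, 14. Dose days are taken at their nominal dates.
- On-treatment chemistry: D15 ±3, that is D12 to D18.
- Gap *g* from registration to dose 1: the protocol gives no maximum. The minimum is 0; I also show 14 days as an assumption.
- Standard for the hold rule: prior-week blood, read as 7 days or less.

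**Step 1, windows.** A panel drawn 15 to 28 days before registration passes 8.1 and Section 10 and fails 6.2, reading study entry as registration. A panel drawn within 14 days passes both.

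**Step 2, cycle 1.** Age of newest required creatinine at a dose = *w* + *g* + *d*.

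| Case | D1 | D8 |
|---|---|---|
| Schedule alone, *w* = 28 | 28 + *g* | 35 + *g* |
| 6.2 enforced, *w* = 14, *g* = 0 | 14 + 0 + 0 = 14 | 14 + 0 + 7 = 21 |
| 6.2 enforced, *w* = 14, *g* = 14 (assumed) | 14 + 14 + 0 = 28 | 14 + 14 + 7 = 35 |

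If study entry means the start of treatment, *g* drops out and the ages are 14 and 21 days. These are the oldest values allowed; a patient may have a newer one.

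**Step 3, D15 of cycle 1.** The first on-treatment panel falls 11 to 17 days after dose 1. If it is drawn and reported before the D15 dose, that dose is covered. If not, the newest required value can be 14 + 0 + 14 = 28 days old at *g* = 0.

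**Step 4, later cycles.** From D15 to the next D1 is 22 − 15 = 7 days nominally (4 to 10 with the draw window). From D15 to the next D8 is 29 − 15 = 14 days (11 to 17). So D1 of later cycles is nominally covered and D8 is not.

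**Step 5, is aligning the window enough?** No. With *w* = 14 everywhere, the ages are still 14 + *g* at D1 and 21 + *g* at D8, both above 7. The second problem needs added chemistry.

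**The case against.** The best defense is that nothing here is unworkable. Both windows can be met with one panel inside 14 days. Section 6.2 binds, and 15.2 requires a signed eligibility checklist. Chemistry once per cycle is a deliberate rule, stated consistently in 4.3.1, 9.0 and Section 10, and the D15 panel is the prior week's blood for the next D1. The prior-week phrase introduces several hold rules at once and may have been written with the CBC in mind. Dose 1 is governed by eligibility and a required baseline panel, and 6.3 excludes renal dysfunction that makes cisplatin unsafe. Section 10 allows extra tests when clinically indicated, and the institutional guideline cited in 4.3.1 may ask for more.

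Much of this stands. It shows that careful staff can run the trial safely. It does not make the schedule agree with 6.2, and leave to test is not a requirement. The creatinine hold is listed under the prior-week lead-in, so as written it calls for data that are not scheduled.

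Three stronger readings are tempting but unsupported:
- **Renal injury from recent platinum will be missed.** Prior platinum is allowed, prior chemotherapy may end 7 days before entry, and 11.2 puts onset at 14 days. But 11.2 states that onset alongside a single 50 mg/m² dose, and the scenario needs a panel drawn before the last platinum, no repeat test, and fixed dates that ignore the ±3 days on dose 2. It does not prove harm.
- **No cycle 1 dose is covered.** This assumes that the D15 panel cannot guide the D15 dose. The text says that it informs the next cycle; it does not bar earlier use, and a draw on D12 to D14 is prior-week blood.
- **Entry with creatinine above 1.5 mg/dL, which 6.2 allows if clearance is at least 50 cc/min, is left unhandled.** Section 4.3.1 handles it by delay, hydration and recheck.

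**Conclusion.** The point holds as a conflict between eligibility and schedule, and as a renal hold rule without required data for some doses. A panel from days 15 to 28 fits the schedule but cannot establish eligibility. Doses without required prior-week chemistry are cycle 1 D1 and D8 and the D8 dose of later cycles; D15 depends on when its panel is reported. The cycle 1 ages rest on reading study entry as registration, on 6.2 being enforced, and on no gap before dose 1; any gap makes them larger. The number of patients affected cannot be derived from the documents. This is a safety and consistency matter that should be corrected, not a threat to the trial's statistical conclusions.

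**What to change.** 1. In 8.1 and the Section 10 table, give the CBC and the metabolic panel with magnesium their own 14-day window, and leave imaging, biopsy and visits at 28 days. State that study entry means registration, if that is the intent. Reword 4.2 so that the fixed 25 mg/m² first dose is given if labs within 14 days meet the 6.2 limits.
2. Require a metabolic panel with magnesium within 7 days before dose 1. For all patients, add creatinine to the pre-dose CBC at D8 of each cycle, or preferably to every weekly CBC. Require that the D15 panel be drawn and reviewed before the D15 dose. Limiting the D8 test to recently platinum-treated patients would leave the same gap for everyone else.

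**Cost.** A short amendment: a line in 8.1, a footnote and a few cells in the Section 10 table, one reworded sentence in 4.2, and a clause in 4.3.1. Cycle 1 adds at most 2 routine tests per patient, or 2 × 54 = 108 at the current accrual target. Each later cycle adds one (D8), or two (D1 and D8) if creatinine joins every weekly CBC. The total depends on the number of cycles, which the protocol does not fix. The blood can come from CBC or research draws already scheduled, but results must be back before the infusion. Repeating labs that are 15 to 28 days old is no new burden, because 6.2 already demands it.
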